The pharmacological armamentarium in cluster headache consists of acute / abortive therapies, transitional therapies and preventive treatments. First line of acute treatment is sumatriptan administered subcutaneously^{10, 11, 12} and inhalation of 100% oxygen.^{13, 14, 15, 16} Transitional therapies are often used to relieve the patient until the preventive agents are adequately titrated, and consists of oral steroids or greater occipital nerve (GON) blocks.^{17, 18} The currently available preventive pharmacological treatments are unspecific, insufficient, and hampered by side-effects. Preventive treatment aims to reduce attack frequency with verapamil being first-choice, but only 50 to 80% of cluster headache patients are responders,¹⁹ and its use is hampered by side-effects since many patients need high doses. Other preventive treatments are less attractive due to their side-effect profile, the scarcity of evidence^{20, 21} and high cost.²² In the clinic, several types of treatment are combined in the effort to provide relief to the patients and improve the quality of life.

Increased plasma or serum levels of calcitonin gene-related peptide (CGRP) have been associated with painful syndromes such as migraine and cluster headache.²³ Cluster headache patients have higher CGRP levels compared to migraine patients and healthy controls.²⁴ As in migraine,²⁵ CGRP levels are altered during attacks. Recently, a provocation study supported the central role of CGRP involvement in cluster headache as infusion of CGRP induced attacks in patients with cCH and in patients with episodic cluster headache in an active bout.²⁶

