Appendix II

Recent and Concomitant Medication

Disallowed or Allowed with Restrictions

Recent and Concomitant Medication: Disallowed or Allowed with Restrictions

In the table below, recent and concomitant medications that are disallowed or allowed with restrictions with respect to their use prior to or during the study are listed.

Drug Class	Details
Any investigational drug	Do not use within 30 days or 5 plasma half-lives (whichever is longer) prior to the Screening Visit.
Anticonvulsants	
Anticonvulsants can only be used for preventive treatment for cluster headache and are allowed with restrictions- see Cluster Headache Therapies.

Cluster Headache Therapies

• **Abortive treatment**

The following abortive therapies for cluster headache attack are allowed at any time during the study:

- High-flow oxygen;
- Oral triptans, sumatriptan subcutaneous injection; sumatriptan nasal spray; zolmitriptan nasal spray;
- Acetaminophen, non-steroidal anti-inflammatory drugs (NSAIDs);
- Dihydroergotamine (allowed for not more than 3 times per week) or ergot derivatives;
- Octreotide.
- Opioids are allowed with restrictions (maximum 2 days per week).
- Cannabinoids are allowed if prescribed or if locally approved

• **Transitional treatment**

Disallowed for 30 days prior to the Screening Visit and during the Screening Period:

- Greater occipital nerve block;
- Injected and oral steroids (used for headache treatment).

• **Preventive treatment:**

Stable dose (with restriction on the maximum dose for lithium only) for 1 month prior to the Screening Visit and during the Screening Period:

- Verapamil;
- Topiramate;
- Gabapentin;
- Valproate;
- Candesartan;
- Lithium: the maximum dose must be as per the country-specific guidelines for management of patients with CH **AND** the se-lithium level must be below the toxic serum level of lithium, based on the reference ranges of the local laboratory;
- Indomethacin.

Initiation, discontinuation, and change of dose are allowed during the Treatment Period and the SFU Period.

At any time:

- Melatonin

Initiation, discontinuation, and dose modifications are allowed during the Treatment Period and the SFU Period.

Dihydroergotamine is disallowed for use as a preventive treatment.

• **Other treatment and interventions:**

Disallowed for 4 months prior to the Screening Visit and until the SFU Visit:

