- Botulinum toxin type A or B, administered in the head or neck area for treatment of cluster headache or other disorders, or for cosmetic use.

Disallowed for 30 days prior to the Screening Visit and until the SFU Visit:

Drug Class	Details
	
– any other cranial or extracranial nerve block;– any neuromodulation treatment;– gamma knife or other invasive procedures.
Anti-CGRP therapies	Anti-CGRP therapies are disallowed for ≤ 5 half-lives for mAbs and ≤ 1 month for gepants prior to the Screening Visit.
Antihypertensives	
• Candesartan and Verapamil allowed with restrictions- see Cluster Headache Therapies 
Other medications in the same class are allowed.

Anti-impotence agents	Allowed if the dose has been stable for at least 12 weeks prior to the Screening Period and remains stable until the Completion Visit (Week 48).
Cannabinoids	Allowed with restrictions- see Cluster Headache Therapies .
COVID-19 vaccine	Allowed with restrictions: 
• If possible, COVID-19 vaccine should not be administered < 14 days prior to the Screening Visit.• If possible, COVID-19 vaccine should not be given within ± 3 days of eptinezumab infusion.
Ergot alkaloids	
• Methergine is disallowed for 14 days prior to the Screening Visit and until the SFU Visit. 
Other medications in the same class are allowed.

Steroids: Oral and Injectable	Allowed with restrictions: 
• For transitional treatment for CH, see Cluster Headache Therapies• For indications other than cluster headache:
• Disallowed during the Screening Period• Short-term treatment (maximum 3 days, followed by potential tapering) is allowed from Baseline until the SFU Visit
Illicit substances	Disallowed for 2 months prior to the Screening Visit and until the SFU Visit: Psilocybin (mushrooms), lysergic acid diethylamide (LSD), or 2-bromo-LSD, or other illegal drugs.

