13.5 Analysis Methodology for the Secondary and Exploratory Endpoints

13.5.1 Short-term Efficacy Estimand

The short-term efficacy estimand is the mean change from Baseline in the weekly number of attacks (Weeks 1-4) for participants with chronic cluster headache receiving IV infusion of eptinezumab 400 mg every 12 weeks, without the use of transitional treatment (GON block and oral steroids), and regardless of the use of abortive and preventive medication for cluster headache, and infusion interruption or termination before full dose is received.

Clinical Question of Interest

The clinical question of interest is changes in cluster headache symptoms within the first 4 weeks after infusion with eptinezumab 400 mg.

Attributes of the Short-term Efficacy Estimand

The short-term efficacy estimand has the following attributes:

- The **treatment condition of interest** will be IV infusion of eptinezumab 400 mg every 12 weeks, with or without the use of abortive and preventive medication for cluster headache
- The **population of interest** will be participants with cCH
- The **endpoint to be obtained to address the clinical question** is change from Baseline in the weekly number of attacks (Weeks 1-4)
- The **intercurrent event** use of transitional treatment will be addressed by a hypothetical strategy estimating the efficacy, in the hypothetical scenario where no transitional treatment is available, while interruption or termination of IMP such that full dose is not received will be addressed by a treatment policy strategy
- The **population level summary** will be the mean change across weeks 1-4

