13.5.1.1 Rationale for the Short-term Efficacy Estimand

The number of weekly attacks is considered a good measure of the impact of IV infusion of eptinezumab 400 mg every 12 weeks, since it captures an important part of the symptoms for cluster headache and therefore change from Baseline in the average number of weekly attacks will be used as the endpoint for the efficacy estimand described in details in section 13.5.1.

Justification of Treatment Condition of Interest

The use of abortive medication (triptans and oxygen) is included in the treatment condition of interest because abortive medication is taken after an attack begins to affect that specific attack. It is not expected that the use of abortive medication will affect the number of attacks following an attack where abortive medication was taken. Thus, the use of abortive medication is not considered to be an intercurrent event.

The use of preventive medication is included in the treatment condition of interest because eptinezumab is expected to be used with or without other preventive medication for participants suffering from chronic cluster headache. Furthermore, though the use of preventive medication could influence the number of attacks, the potential effect is expected to be limited in a chronic cluster headache population. Thus, the use of preventive medication is not considered to be an intercurrent event.

Intercurrent Events

The following intercurrent events, occurring after treatment initiation and potentially affecting either the interpretation or the existence of the measurements associated with the clinical question of interest, are considered.

- Use of transitional treatment (GON block and oral steroids) – hypothetical strategy

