Use of transitional treatment could change the disease status considerably, and thus influence the number of attacks. In a study, 35% of the participants taking the oral steroid prednisone experienced a complete cessation of cluster headache attacks after 7 days compared to 7% in the placebo group and 49% taking prednisone experience at least a 50% reduction of cluster headache attacks compared to 15% for the placebo group after 7 days.¹ To get a clearer picture of the change in symptoms after infusion with eptinezumab, a hypothetical strategy has been chosen to address this, estimating the effect if no transitional treatment was available, using the 7 day limit¹ as described in section 23.2.1.5. Due to the expected positive effect of transitional treatment this is considered a conservative approach.

- Interruption or termination of IMP such that full dose is not received – treatment policy strategy

If an IMP is stopped prematurely (either temporarily or completely) the consequence is that the participant did not receive all of the intended dose of eptinezumab and it could be expected that the potential effect of eptinezumab could be decreased due to the lower dose. To be conservative, a treatment policy strategy is used to address this.

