23.2.1.5 Calculation of Assessments for Intercurrent Events

Withdrawal from Treatment

When considering withdrawal from treatment data that are collected 3 months or more after the latest infusion will be excluded. Thus, for the daily entries, data occurring 84 days or more after the date for withdrawal from treatment will be removed. For the weekly entries, if at least one day of the 7-day period is covered by 84 days or more then data will be removed.

Use of Transitional Treatment

When considering the use of transitional treatment, data are excluded 7 days after the use of transitional treatment. Thus, for the daily entries, data that occur on 1 to 7 days after the date of use of transitional treatment will be removed. For the weekly entries, if the 7-day period is including at least 1 of the days in the 7-day period after use of transitional treatment data will be removed.

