23.2.4 Use of Transitional Treatment

To address the endpoint Use of transitional treatment (Weeks 1-48), use of a transitional treatment will be collected from the “Transitional and Preventive Treatment for Cluster Headache Log” and in case of no findings, a participant will get a corresponding value of 0 for number of times a transitional therapy was used.

If a participant withdraws, any transitional treatment that is collected from the form will be considered up until 48 weeks after the first IMP infusion.

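### The SAP leaves unclear whether diary days after injected headache steroids are removed, and has no rule for days after steroids given for other conditions

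*SAP*

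**What the plan says.** **Estimand wording.** SAP 13.5.1 defines the short-term estimand "without the use of transitional treatment (GON block and oral steroids". Section 13.5.1.1 lists the intercurrent event as "Use of transitional treatment (GON block and oral steroids", under a hypothetical strategy. Section 13.5.3 uses the same two items for the long-term estimand.

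**Protocol wording.** Appendix II places two entries under transitional treatment: GON block, and "Injected and oral steroids (used for headache treatment". Both are barred only for the 30 days before screening and during screening, so both can be used in the Treatment Period. Protocol 1.1.1 is narrower and says that transitional therapy "consists of oral steroids or greater occipital nerve (GON) blocks".

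**Removal rule.** SAP 23.2.1.5 says, for daily entries, that "data that occur on 1 to 7 days after the date of use of transitional treatment will be removed". A weekly entry is removed if any of its days falls in that window. For the source, SAP 23.2.4 says that "use of a transitional treatment will be collected from the" log kept for transitional and preventive cluster headache treatment. The definitions of DPS2 and DPS3 in SAP chapter 6 refer to 23.2.4. Neither 23.2.1.5 nor 23.2.4 lists drugs.

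**Steroids for other conditions.** Appendix II states: "Short-term treatment (maximum 3 days, followed by potential tapering) is allowed from Baseline until the SFU Visit". It gives no length for the taper.

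**Reason for the rule.** SAP 13.5.1.1 argues that transitional treatment can change the number of attacks and cites a prednisone trial in which "35% of the participants taking the oral steroid prednisone experienced a complete cessation of cluster headache attacks after 7 days", against 7% on placebo. For a reduction of at least 50% the figures are 49% and 15%.

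**The concern.** Both efficacy estimands are meant to describe the change in attacks without transitional treatment. That requires a clear list of what triggers removal, and the documents give two lists plus a derivation with none. Two programmers could build different DPS2 and DPS3 datasets from the same text.

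The second gap concerns the rationale. The argument for removal is about what the drug does to attack counts, and that does not depend on why the drug was prescribed. The SAP explains why abortive and preventive medication are not intercurrent events. It says nothing about steroids for other conditions. If such courses lower attack counts, the retained days are credited to eptinezumab, and a single-arm trial has no control group to offset this. The SAP calls its approach conservative because transitional treatment is expected to help; unremoved steroid days work the other way.

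**Working it through.** The plan states no figure for the diary days affected, so there is none to reproduce. The check is a comparison of text, followed by an illustration of size.

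**1. Injected steroids used for headache**

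- SAP 13.5.1, 13.5.1.1 and 13.5.3: GON block, oral steroids.
- Protocol 1.1.1: GON block, oral steroids.
- Protocol Appendix II: GON block, oral steroids, injected steroids.
- SAP 23.2.1.5 and 23.2.4: whatever the log holds as transitional treatment.

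Read by the estimand text, days after an injected headache steroid stay in. Read by the derivation sections together with Appendix II, they come out. SAP chapter 22, which lists changes from the protocol, does not mention the narrower wording.

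**2. Steroids for other conditions**

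The route is: permitted by Appendix II; recorded as concomitant medication (Protocol section 7); not expected in a cluster headache log; hence no trigger under 23.2.4; hence no removal under 23.2.1.5. The days stay in DPS2 and DPS3. No other SAP rule removes them.

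**3. Whether a planned analysis would show it**

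The sensitivity analysis in SAP 13.5.9.1 puts all data back in. It never widens the exclusion. SAP chapter 10 lists transitional and disallowed medications separately; permitted steroids for other conditions are neither, so they appear only in the general medication summaries.

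**4. Size, for illustration**

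From the SAP's prednisone figures, the excess over placebo is 35 - 7 = 28 points for cessation and 49 - 15 = 34 points for a reduction of at least 50%. SAP reference 1 is a trial in episodic cluster headache.

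For Weeks 1-4, shift in mean change = f x (w/4) x r x B, where:

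- f = share of participants with an unremoved course in that window: 2-10% (assumed; the documents give no rate)
- w = weeks affected: 1-2 (assumed)
- r = extra proportional reduction: 0.31-1.0 (assumed). The 0.31 credits cessation as 100%, other responders as 50% and the rest as 0: prednisone 0.35 + 0.14 x 0.5 = 0.42; placebo 0.07 + 0.08 x 0.5 = 0.11; difference 0.31. This is a crude value, not a lower bound.
- B = baseline weekly attacks: 3.5-14. The lower end is the entry minimum, 14/4 = 3.5; the upper end is assumed.

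Results in attacks per week:

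- Low: 0.02 x 0.25 x 0.31 x 3.5 = 0.005
- Middle: 0.05 x 0.25 x 0.5 x 7 = 0.044
- High: 0.10 x 0.5 x 1.0 x 14 = 0.70

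For Months 1-12 the same courses are spread over 48 weeks, and the monthly baseline is 4B. If f is now the share with one course in the year, the middle case is 0.05 x (1/48) x 0.5 x 28 = 0.015 attacks per month and the high case is 0.10 x (2/48) x 1.0 x 56 = 0.23. These sums ignore prorating and the MMRM.

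**5. Remission and conversion**

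SAP 23.2.1.9 requires at least 4 consecutive weeks and allows one missing week. SAP 23.2.1.8 requires 12 weeks in its first line and 13 in its list of criteria, with at least 7 observed, so a 13-week series may contain 13 - 7 = 6 missing weeks. Removal can therefore create a success: the sequence attack-free, removed week that had attacks, attack-free, attack-free meets the remission criteria. This applies if these endpoints use DPS3, as SAP 13.5.4 implies. Section 13.5.6.3 instead sends them to the descriptive methods, for which chapter 6 names DPS1.

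**The case against.** The strongest reply has four parts.

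*The operative rule is wide enough.* A reader might infer from the estimand wording that counts under injected headache steroids are certainly kept. The documents do not show that. The derivation sections have no drug list, and Appendix II classes these injections as transitional, so a logged injection would probably trigger removal. The parenthesis may be shorthand. This stands: the point is an unresolved inconsistency, not demonstrated retention.

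*Courses for other conditions are limited.* Appendix II allows short courses only, exclusion criterion 18 bars patients expected to need restricted medication, and criterion 17 covers other relevant disorders, including pulmonary ones. This stands as a reason to expect few courses. It does not give a count, and the taper length is open.

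*Scope is a choice.* The hypothetical scenario is one without transitional treatment, and the SAP knowingly keeps other drugs that may influence attacks, such as preventives. Keeping incidental medication is defensible. This stands as a reason to use a sensitivity analysis and leave the main estimand unchanged on this point. The SAP should still state its choice.

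*Stakes are modest.* Safety is the primary objective, efficacy is secondary, and no formal testing is planned. This is true, and it limits the weight of the point.

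**Conclusion.** The concern holds in a limited form. The definition of transitional treatment differs between the estimand text and Appendix II, and the derivation sections do not settle it. Diary days after steroids for other conditions stay in DPS2 and DPS3, against the SAP's own reasoning. The direction favours eptinezumab if such courses lower attack counts as the SAP expects.

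The size cannot be derived from the documents. Under the assumed inputs the Weeks 1-4 shift runs from 0.005 to 0.70 attacks per week, with about 0.04 in the middle case; the upper end needs every input at its extreme. It is probably small unless such use is common.

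Two stronger readings are not supported:

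- A reader might take the 28-point excess to mean that about one in four unremoved courses yields an attack-free week, and multiply by an assumed 2-10% exposure to get 0.6-2.8% of participants. The exposure is assumed, and the 28 points come from prednisone in episodic cluster headache, not from short courses for other conditions in chronic patients.
- A reader might infer that remission and conversion are materially inflated by retained steroid days. A short course would seldom produce 4 attack-free weeks, let alone 12 or 13. For these endpoints the clearer risk is the removal rule itself, because a deleted week can bridge a run.

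**What to change.** 1. Use one definition in SAP 13.5.1, 13.5.1.1, 13.5.3, 23.2.1.5 and 23.2.4, aligned with Appendix II: GON block, and oral or injected steroids used for headache.
2. State that steroids for other indications are not an intercurrent event in the main analysis, and why. Identify systemic courses from the coded concomitant medication data (ATC code, start and stop dates, and route where recorded) and report how many participants had one.
3. Add a sensitivity analysis of the short-term and long-term estimands that applies the exclusion from the start of each such course to 7 days after its last dose. Leave out local injections for other conditions.
4. For remission and conversion, do not let a removed week that contained attacks count as a permitted missing week.

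The endpoint on use of transitional treatment can stay limited to headache use. The cost is SAP wording, one extra lookup in data already collected, and a few more diary days lost in the sensitivity analysis. No change to clinical management is involved.

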13.5.1.1.1 Missing Data

Details of imputation of missing data are provided in section 23.2.1.3.

13.5.1.2 Estimator

To estimate the change from Baseline in the number of weekly attacks (Weeks 1-4) described above, a Mixed Model for Repeated Measurements (MMRM) using a restricted maximum likelihood (REML)-based approach will be used. The data used for the MMRM is FAS and DPS2. The MMRM will include the following fixed effects: week (1, 2, 3, 4, 13, 14, 15, 16, 25, 26, 27, 28, 37, 38, 39, 40), and country (for details see section [23.2.3](#)) as factors, logarithm of the baseline score as a continuous covariate, and the logarithm of the baseline score-by-week interaction. An unstructured covariance structure will be used to model the within-participant errors. The Kenward-Roger approximation will be used to estimate denominator degrees of freedom. The change from Baseline in the number of weekly attacks (Weeks 1-4) will be estimated as the average from the least squares estimates from the MMRM for the week effect using the contrast [1, 1] [1, 2] [1, 3] [1, 4] /divisor = 4. The SAS® code for the analysis is shown in [Appendix II](#). If this analysis fails to converge the following covariance structures will be tried out:

- UN(15) - banded unstructured
- UN(14) - banded unstructured
- UN(13) - banded unstructured
- UN(12) - banded unstructured
- TOEPH – heterogenous Toeplitz
- CSH – heterogenous compound symmetry
- TOEP - Toeplitz
- CS - Compound Symmetry

and the one with the lowest AIC amongst the ones that converged will be applied. In case of no models converging, the results will only be shown as described in chapter [7](#).

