1.3 Exploratory Objective

To explore the target engagement of eptinezumab to CGRP.

2 Trial Design

This is an interventional, open-label, fixed-dose multiple administration trial to evaluate the long-term treatment with eptinezumab in participants with cCH.

An overview of the trial is presented in [Panel 1](#) and the scheduled trial procedures and assessments are summarized in [Appendix IV](#).

The target population for this trial is defined as participants with cCH, based on the *International Headache Society* International Classification of Headache Disorders third edition (IHS ICHD-3) classification, with documented evidence of cCH prior to screening and confirmed via prospectively-collected information in the eDiary during the Screening Period. A minimum of 14 cluster headache attacks must be captured in the eDiary for the 28-day Screening Period.

The total trial duration from the Screening Visit to the Safety Follow-up (SFU) Visit is approximately 60 weeks and includes Screening Period (4 weeks), Treatment Period (48 weeks), and SFU Period (8 weeks).

Eligible participants will receive four infusions with eptinezumab 400 mg at 12-week intervals at Day 0 (Visit 2), at the end of Weeks 12 (Visit 5), 24 (Visit 8) and 36 (Visit 11), administered as an intravenous (IV) infusion of 45 minutes (+15 minutes).

The SFU Visit will take place at Week 56 (Visit 15); that is, 20 weeks (5 half-lives) after the last eptinezumab administration.

Participants who withdraw from study, except for those who withdraw their consent, will be asked to attend a Withdrawal Visit as soon as possible and a further SFU Visit, scheduled 20 weeks (5 half-lives) after the last eptinezumab administration.

Participants who are withdrawn from the treatment will be given the opportunity to remain in the trial at the discretion of the investigator. Participants will be expected to attend all scheduled trial visits and procedures except eptinezumab administration. If participants refuse, they will be asked to attend a Withdrawal Visit as soon as possible and a further SFU Visit, scheduled 20 weeks (5 half-lives) after the last eptinezumab administration.

Eligibility will be assessed during the Screening Period and before the first administration of eptinezumab at the Baseline Visit (Day 0/Visit 2).

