13.1 General Efficacy Analysis Methodology

All confidence intervals (CIs) will be two-sided 95% CIs.

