Appendix II

SAS® Code

SAS® Code

Short-term Efficacy Estimand

The SAS® code for the analysis of the short-term efficacy estimand described in Section 13.5.1 is given below. Here it is assumed that the ordering of the week factor is week 1, week 2, week 3, week 4, ...

```
proc mixed data=DPS2 method = REML noclprint;
  class COUNTRG1(ref = "OTHER") AVISITN USUBJID;

  model CHG = COUNTRG1 AVISITN LOGBASE LOGBASE*AVISITN / DDFM = KR;

  repeated AVISITN / type=UN subject=USUBJID;

  lsmeans AVISITN 'Change from Baseline in Weekly Attacks: Weeks 1-4'
    [1, 1] [1, 2] [1, 3] [1, 4] / divisor = 4;

run;
```

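### In this single-arm trial the baseline-adjusted MMRM intervals treat the sampled baseline mean as known, so the 95% CI is too narrow for the mean change in the cCH population

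*SAP*

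**What the plan says.** SAP chapter 2 describes a single treated group: "This is an interventional, open-label, fixed-dose multiple administration trial to evaluate the long-term treatment with eptinezumab in participants with cCH". In SAP 13.5.1 the population of interest "will be participants with cCH" and the population-level summary "will be the mean change across weeks 1-4".

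The estimator in SAP 13.5.1.2 is an MMRM of change from baseline with week and country as factors, the "logarithm of the baseline score as a continuous covariate, and the logarithm of the baseline score-by-week interaction", an unstructured covariance and Kenward-Roger degrees of freedom. The result "will be estimated as the average from the least squares estimates from the MMRM for the week effect". The code in SAP Appendix II is "model CHG = COUNTRG1 AVISITN LOGBASE LOGBASE*AVISITN / DDFM = KR". It leaves the covariate at its default value, the sample mean, and weights the country levels equally. No step allows for sampling error in the baseline mean.

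SAP 13.1 sets the level: "All confidence intervals (CIs) will be two-sided 95% CIs". SAP 13.5.2 (Weeks 1-2) and 13.5.3 (Months 1-12) reuse the estimator. So does 13.5.6.1 for the eDiary endpoints, the SIS domains, the EQ-5D-5L VAS and the WPAI sub-scores, with baseline log-transformed for attack counts and the integrated pain measure and untransformed otherwise. PGIC is modelled without a baseline term. SAP 13.2 rules out formal testing.

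**The concern.** In a randomised comparison both arms are evaluated at the same baseline value, so the baseline contribution largely cancels from the difference and adjustment sharpens it. With one arm nothing cancels. The LS mean depends on which baselines happened to be sampled, and another sample of cCH patients would have a different mean log baseline and hence a different mean change. The model-based standard error contains only the residual variance left after baseline is removed. Kenward-Roger does not supply the missing part, because it allows for estimated covariance parameters and not for a random covariate mean.

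A non-zero slope is to be expected. Change is post-treatment minus baseline, attack counts cannot fall below zero, and entry requires at least 14 attacks in 28 days. SAP 13.5.7 itself gives accounting for the baseline level as a reason for the model. With no testing planned, the interval is the main inferential output of these models, so what is at stake is overstated precision of the efficacy estimates.

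**Working it through.** **Inputs from the documents.** One arm (SAP chapter 2); two-sided 95% CI (13.1); log baseline, its interaction with week, and country in the model (13.5.1.2, Appendix II); countries with fewer than 20 participants pooled (23.2.3); entry floor of 14 attacks in 28 days, that is 14/4 = 3.5 per week. The planned number treated (SAP chapter 20) reproduces: 100/(1 − 0.20) = 125. The plan states no SD, slope, R² or target CI width.

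**Formula.** Take complete data and, for the moment, no country term. The Week 1-4 contrast is then the fitted participant-level mean change at the sample mean of log baseline, which equals the raw mean change. Write b for the slope on log baseline averaged over Weeks 1-4.

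- Variance used by the model: s²_res / n
- Variance for the mean in the cCH population: (s²_res + b² × Var(log baseline)) / n = s²_total / n
- With R² = b² × Var(log baseline) / s²_total, the ratio of the model SE to the correct SE is sqrt(1 − R²)
- Coverage = 2Φ(1.96 × sqrt(1 − R²)) − 1

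| Assumed R² | SE ratio | Coverage of nominal 95% CI | Widening needed |
|---|---|---|---|
| 0 | 1.00 | 95.0% | 1.00 |
| 0.05 | 0.97 | 94.4% | 1.03 |
| 0.10 | 0.95 | 93.7% | 1.05 |
| 0.20 | 0.89 | 92.0% | 1.12 |
| 0.30 | 0.84 | 89.9% | 1.20 |
| 0.40 | 0.77 | 87.1% | 1.29 |

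For example, at R² = 0.05: sqrt(0.95) = 0.975, 1.96 × 0.975 = 1.91, and 2Φ(1.91) − 1 = 94.4%.

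**Country factor.** Equal weighting of unequal countries raises the printed SE. For an assumed split of 20/20/25/60 the factor is sqrt(125 × (1/20 + 1/20 + 1/25 + 1/60) / 4²) = sqrt(1.224) = 1.11. That would offset the narrowing at R² = 1 − 1/1.224 = 0.18, if the estimator stayed as precise as the raw mean. It does not, as the simulation shows.

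**Simulation.** n = 125, 3,000 replicates per scenario, assumed log-normal baselines of at least 3.5 attacks per week, country shares 16/16/20/48%. A participant-level ANCOVA stands in for the MMRM contrast with complete data.

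| R² | Coverage, no country | Coverage, with country | Coverage, raw-mean t interval |
|---|---|---|---|
| 0.04 | 94.2% | 95.6% | 95.0% |
| 0.05 | 94.6% | 94.5% | 95.7% |
| 0.15 | 92.5% | 93.5% | 94.7% |
| 0.22 | 90.9% | 91.5% | 94.3% |
| 0.33 | 89.1% | 89.8% | 94.8% |
| 0.41 | 85.9% | 87.2% | 93.5% |

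At R² = 0.15 the printed CI with country (mean width 1.81) is as wide as the raw-mean CI (1.78). But the country-weighted estimate is itself more variable (empirical SD 0.485 against 0.450) and needs about 2 × 1.96 × 0.485 = 1.90. With n = 100 the pattern is the same.

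**Does the added term repair it?** In a second simulation at n = 125, with and without country, the specified interval covered 92-94% at R² of 0.03-0.05, 90-93% at about 0.20 and 86-87% at 0.41. Adding b² × Var(log baseline)/n brought coverage to 94-96%, or about 93.5% in the most skewed case.

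**The case against.** The strongest reply is that conditioning on observed covariates is ordinary regression inference, and that the interval is valid for the mean change given the baselines seen. That is correct. Participants are also not a random draw from all cCH patients: they come from specialist settings and pass attack-frequency and diary-compliance filters. But the SAP does not say that its CIs are conditional, and its estimand names the cCH population, so the narrower reading is not the one the document gives.

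The second reply is that the size is unknown, and this stands. A reader might infer that change is strongly tied to baseline and that the intervals are badly wrong. The documents give no SD, slope or R² to support that, and at an R² of about 0.05 the loss is negligible.

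A reader might also infer that every continuous efficacy result is affected and has no other statement of uncertainty. That goes too far. PGIC has no baseline term. SAP chapter 7 gives n, mean and SD, from which an unadjusted SE follows, although those summaries use all data points (DPS1) and not the sets used for the estimands (DPS2, DPS3), so they are only an approximate check.

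Finally, the consequences are limited. The primary objective is safety, no hypothesis is tested, there are no key secondary endpoints, and no stated decision rests on these intervals. In an uncontrolled open-label trial no CI width addresses causal uncertainty.

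**Conclusion.** The point holds as a matter of direction. As specified, the two-sided 95% CI for the LS-mean change is too narrow for the mean change in participants with cCH whenever change depends on baseline, by about sqrt(1 − R²). Over an assumed R² of 0.05 to 0.40, coverage is about 94% down to about 87%. The calculation assumes that participants are treated as a sample from the target population and that data are complete; the simulations further assume log-normal baselines. Equal country weights can widen the printed interval but do not restore coverage.

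It affects 13.5.1.2, 13.5.2, 13.5.3 and the baseline-adjusted models in 13.5.6.1. It does not affect PGIC, the primary safety objective or any type I error rate, and it is not a criticism of the point estimates. It is worth correcting because the correction is cheap.

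**What to change.** Keep the MMRM and its point estimates. In SAP 13.5.1.2, state that SEs and CIs allow for sampling variation in baseline, by one of two routes:

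- Add the missing term to the squared model SE. For the Week 1-4 contrast this is the squared average slope on log baseline over Weeks 1-4, times Var(log baseline)/n. Other contrasts use the average slope over their own weeks or months, and endpoints with untransformed baseline use that baseline.
- Bootstrap participants, refitting with the covariance structure already selected so that the convergence and AIC sequence is not repeated in each resample.

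Apply the same rule to 13.5.2, 13.5.3 and the baseline-adjusted models in 13.5.6.1.

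Refitting with baseline as the first response is not recommended. It drops the log-baseline covariate that SAP chapter 22 specifies and changes the estimates. It also enlarges the unstructured matrix from 16 × 17/2 = 136 to 17 × 18/2 = 153 parameters, for about 125 participants.

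Cost: a short SAP paragraph, a little programming and slightly wider CIs. No data collection or clinical procedure changes.
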